**\*\*If yes complete the following:**

a. The LSCDVAMC investigator will send:

- Hardcopy information or specimens  
 Electronic information

b. What are the procedures for transporting and/or transmitting identifiable information securely?

c. What will be the final disposition of the identifiable data transferred offsite?

- Record Control Schedule 10-1 indicates that all research records must be retained indefinitely

All identifiable data transferred to the LSCDVAMC will be maintained in accordance with the local record control schedule in a secure location in the motion study lab office B-B322. Since no subjects will receive an implant in this study their information will be destroyed at the end of this study.

62. Record Control Schedule 10-1 indicates all research records must be retained indefinitely. Please indicate where this information will be stored and the safe guards to protect it:

a. Electronic Safeguards:

- No electronic data will be stored  
 VA encrypted laptop  
 Encrypted VA device/media- describe:  
 VA network drive;  
 M: drive; whose?  
 S: drive  
 Folder access password protected  
 Other drive location (for example P: drive):  
 Folder access password protected

b. Hardcopy safeguards. Two locking barriers must be in place.

- No hardcopy data will be stored  
 Locked Office and Locked File Cabinet

- Coded by Study Staff
- De-identified by Privacy Officer or Statistician
- Other- Describe:

Facility name, address, and room number where hardcopy or electronic data will be stored:  
LSCDVAMC B-B322

### Section 8 – Data and Safety Monitoring – Greater than Minimal Risk Study

- For all research that is greater than minimal risk a Data and Safety Monitoring Plan must be developed.
- This is a plan to assure the research includes a system of appropriate oversight and monitoring of the conduct of the study to ensure the safety of subjects and the validity and integrity of the data.

**\*CHECK BOX IF THIS IS A MINIMAL RISK STUDY  SKIP TO #65**

**63. Safety monitoring for this greater than minimal risk project will include:**

- Data Safety Monitoring Board:
- Data Monitoring Committee
- Other

- *Attach the plan or provide details including whether committee is independent from the study sponsor, how often it meets, whether written reports are available, etc*

**64. Describe the plan for on-site data monitoring by the sponsor, contract research organization (CRO), or other independent body:**

- *\*Research Office must be notified of all on-site monitoring visits.*

**65. Conditions that may result in removal of subjects from the research (check all that apply):**

- |   |   |
|---|---|
|  Medical condition unchanged                |  Medical condition worsened            |
|  Serious adverse event           |  Intolerable complications             |
|  Pregnancy                       |  Investigator's clinical judgment      |
|  Subject withdrawal              |  Subject uncooperative or noncompliant |
|  Study closure by sponsor or FDA |  Refusal to suspend breast-feeding                |
|  Other-describe:                            |  Not Applicable                                   |

**66. If a subject withdraws or is removed from the study, describe the potential risks of early withdrawal and the procedures in place to minimize these risks:**

This is a minimal risk study, thus if subjects withdraw or are removed from the study, there should be no added risk to the subject.

## Section 9 – FDA-Regulated Drugs/Biologics

**NOTE: If this research involves the use of any drugs or biologics, the study is subject to the Food and Drug Administration (FDA) regulations.**

- Documentation of FDA approval for the experimental use of these agents must be provided for review (industry sponsored protocol listing the IND number, letter from the FDA, letter from industry sponsor, or other document and/or communication verifying the IND for this study).
- All drug/biologic products must be dispensed and tracked through the LSCDVAMC Research Pharmacy.
- An M.D. must be part of the Research Team for all studies that involve the use of a device or drugs.
- The LSCDVAMC Pharmacy and Therapeutics (P&T) Committee must approve: (1) Studies of investigational drugs (2) research involving an FDA-approved drug used in a non-approved manner, and (3) an FDA-approved drug, used as approved, when its use is part of a research protocol.
- VA Form 10-9012 Investigational Drug Information Record –must be completed for each drug being evaluated in a research study, regardless of IND status. In addition, the VA Form 10-9012 provides a listing of all authorized prescribers for the study drug(s).

### 67. Type of Product- check all that apply:

- Not Applicable -No FDA-regulated drugs/biologics involved – Proceed to Section 10
- Drug
- Biologic or Other:

### 68. Type of Trial (check as applicable):

- Phase I     Phase II     Phase III     Phase IV     NA

**Phase I Trials:** Initial studies to determine the metabolism and pharmacologic actions of drugs in humans, the side effects associated with increasing doses, and to gain early evidence of effectiveness; may include healthy subjects and/or patients.

**Phase II Trials:** Controlled clinical studies conducted to evaluate the effectiveness of the drug for a particular indication or indications in patients with the disease or condition under study and to determine the common short-term side effects and risks.

**Phase III Trials:** Expanded controlled and uncontrolled trials after preliminary evidence suggesting effectiveness of the drug has been obtained, and are intended to gather additional information to evaluate the overall benefit-risk relationship of the drug and provide adequate basis for physician labeling.

**Phase IV Trials:** Post-marketing studies to delineate additional information including the drug's risks, benefits, and optimal use.

### 69. FDA Status of Drugs/Biologics –

**\* For drugs, an IND may not be necessary if ALL seven of the following conditions are met:**

1. The drug being used in the research is lawfully marketed in the United States;
2. The research is not intended to be reported to FDA in support of a new indication for use or to support any other significant change in the labeling for the drug;
3. The research is not intended to support a significant change in the advertising for the product;
4. The research does not involve a route of administration or dosage level, use in a subject population, or other factor that significantly increases the risks (or decreases the acceptability of the risks) associated with the use of the drug product;

5. The research is conducted in compliance with the requirements for IRB review and informed consent (21 CFR parts 56 and 50, respectively);
6. The research is conducted in compliance with the requirements concerning the promotion and sale of drugs (21 CFR 312.7);
7. The research does not intend to invoke 21 CFR 50.24 (Exception from informed consent requirements for emergency research).

**Provide the following information for each drug/biologic used in this study:**

| Trade and Generic Name | Manufacturer | FDA Approved | Product use consistent with product labeling | IND Required* | IND Number | IND Sponsor or Holder** |
|------------------------|--------------|--------------|--|---------------|------------|-------------------------|
|                        |              |              |  |               |            |                         |

**70. \*\*When the PI holds the IND, complete the following:**

**i. The PI has reviewed the Guidance on Requirements of the Sponsor and the Investigator as Sponsor**

Yes

**ii. As the PI, you will comply with the regulatory responsibilities of a sponsor**

Yes

**71. Drug Information for each drug listed in the protocol -check as applicable**

Approved Drugs

Not Approved

- Attach VA Form 10-9012 Investigational Drug Information Record for each drug used in the protocol
- Attach Package Insert or PDR monograph – copy ready, 8.5 x 11 for each drug listed in the protocol
- Attach Investigator’s Brochure

**72. Provide a detailed description of how FDA-regulated drugs/biologics will be stored, secured, dispensed, administered, tracked, and returned.**

### Section 10 – FDA-Regulated Devices

**This section should be completed for a medical device that is the subject of a clinical study designed to evaluate the effectiveness and/or safety of the device.**

- An investigational device may be an FDA approved device that is being studied for an unapproved use or efficacy. This also includes an approved device that is being studied for an unapproved or approved use in a controlled, randomized, or blinded clinical trial.

- Documentation of FDA approval for the experimental use of the device must be provided for review (industry sponsored protocol listing the IDE number, letter from the FDA, letter from industry sponsor, or other document and/or communication verifying the IDE for this study).

### **Device Risk Determination:**

**Significant Risk (SR) Device** is an investigational device that: (1) is intended as an implant and presents a potential for serious risk to the health, safety, or welfare of a subject, or (2) is purported or represented to be for a use in supporting or sustaining human life and presents a potential for serious risk to the health, safety, or welfare of a subject; or (3) is for a use of substantial importance in diagnosing, curing, mitigating, or treating disease, or otherwise preventing impairment of human health and presents a potential for serious risk to the health, safety, or welfare of a subject; or (4) otherwise presents a potential for serious risk to the health, safety, or welfare of a subject.

**Non significant Risk (NSR) Device** is a device other than a significant risk device.

The IRB is required to document the basis for risk determination based on the proposed use of a device in the research by considering the nature of the harm that may result from the use of the device. FDA has the ultimate decision in determining SR and NSR.

An M.D. must be part of the Research Team for all studies that involve the use of a device.

The Environment of Care Committee (EOC) must approve all research that involves electrically line-operated devices, which have leads or electrodes and will come in contact with human subjects.

**73. Type of Product-check all that apply:**

- Not Applicable -No FDA-regulated devices involved – Proceed to Section 11)**
- An FDA regulated device will be used BUT not with intent of studying safety or efficacy (Proceed to Section 11)**
- Device**

**74. List the device-include name and manufacturer:**

**75. FDA Regulatory Status of the Device:**

- FDA Approved Device**
  - A device approved by the FDA for distribution, marketing, sale to, and use by, the public for the study's indication.
- New Indication of an FDA Approved Device**
  - A device NOT approved by the FDA for distribution, marketing, sale to, and use by, the public for the indication used in the study.
- Investigational - Investigational Device Exemption (IDE)**
  - An FDA designation that permits a manufacturer to lawfully ship an unapproved device for use in a research study.

**Provide the following:**

- a. **IDE Number:**
- b. **IDE Sponsor or Holder:**

**If the PI holds the IDE, complete the following:**

- i. **The PI reviewed the Guidance on Requirements of the Sponsor and the Investigator as Sponsor**

Yes

ii. As the PI, you will comply with the regulatory responsibilities of a sponsor

Yes

c. FDA or Sponsor Device Risk Determination

Non-Significant Risk

Significant Risk

d. Attach documentation of FDA approval for the experimental use of the device (industry sponsored protocol listing the IDE number, letter from the FDA, letter from industry sponsor, or other document and/or communication verifying the IDE for this study).

Humanitarian Use Device (HUD)

- An FDA designation for a medical device intended to benefit patients in the treatment or diagnosis of a disease or condition that affects or is manifested in fewer than 4,000 individuals in the United States per year. For more information about Humanitarian Use Devices see the HRPP SOP manual on the R&D website.

Provide the following:

a. HUD Number:

b. HUD Sponsor or Holder:

c. Include a copy of the FDA letter granting Humanitarian Use Device (HUD) status.

510(k) Status –

- A device determined by the FDA to be “substantially equivalent” to an existing device that is legally marketed in the U.S. Until a 510(k) device is approved, it is still considered investigational.

a. Provide the name of an equivalent device and sufficient documentation to justify 510(k)

76. Attach device information (i.e., brochure, device label)

77. Provide a detailed description of how FDA-regulated devices will be stored, secured, dispensed, administered, tracked, and returned.

## Section 11 – Genetic Testing and Discovery of Genetic Information (DNA)

78. Does the research involve genetic testing or DNA/RNA extraction?

No genetic testing (*Proceed to Section 12*)

Yes- complete the following:

a. Describe the purpose of the genetic testing component of the study

- *Is it to establish risks, associations, or prevalence?*

b. Describe whether the test is a standard test already in clinical use or a new or experimental laboratory study

c. Describe the accuracy of the test

- *Sensitivity, specificity, reliability, validity, and variability*

79. Does an abnormal test result indicate that the subject:

- Has a specific condition
- Is at risk for a specific condition
- May be at risk for a specific condition
- Has, is, or may be at risk for some other outcome
- Other (*describe*):

80. Does a normal test result indicate that the subject

- Is not at risk for a specific condition
- Is at a lower risk for a specific condition
- Is at a population risk for a specific condition

81. Is there a risk of discovery of other results such as non-parentage or other genetic conditions?

- No  Yes- please explain:

82. Will test results produce information on anyone (e.g. a first-degree relative) besides the subject?

- No  Yes- please explain:

83. To whom and in what manner will genetic information be reported?

84. Will genetic counseling be made available to subjects?

No  Yes- indicate who will conduct the counseling and whether there are any additional charges:

85. Will DNA samples be stored?

- No  Yes--describe where, how, and for how long the samples will be stored:

86. Who will own the DNA samples?

87. Will there be any subsequent analysis of the DNA samples?

No  Yes- describe the purpose of the subsequent analysis and whether there will be dissemination of any new information:

88. Describe how samples will be handled if the subject withdraws consent for further participation:

89. Will the samples be distributed to other investigators?

No  Yes- please explain:

90. Describe the provisions to maintain the confidentiality of research data, especially in cases where data can be linked to individual subjects:

### Section 12 – Tissue Collection/Storage/Banking\*

It is VA policy to ensure that human biological specimens, as well as the linked data collected as part of research projects conducted by VA investigators in VA facilities or approved off-site locations, are maintained at \*VA approved tissue banks or VA-sponsored tissue banks.

See VHA Directive 2000-043 “Banking of Human Research Subjects’ Specimens” for more information and also visit [http://www.research.va.gov/programs/tissue\\_banking/default.cfm](http://www.research.va.gov/programs/tissue_banking/default.cfm)

**Human biological specimens (specimens).**

- Human biological specimens are materials, such as blood, urine, tissue, organs, hair, nail clippings, buccal swabs or any other materials that are derived from human subjects and are either collected specifically for research purposes or as residual specimens from diagnostic, therapeutic or surgical procedures.

91. \*Does the research involve storage or banking of human specimens or identifiable private information for use in future studies? (check all that apply)

No (proceed to Section 13)  Yes-describe status of VA approved or VA sponsored facility:

Storing or banking identifiable private information

Storing or banking human specimens

Please provide the following information:

- a. What identifying information will be required?
- b. What are the foreseeable uses of the specimens (e.g., research, pharmaceutical products, production of cellular lines for various uses, etc.)?
- c. What is the VA approved or VA sponsored location/institution where the information and/or specimens will be stored?
- d. How long will the information and/or specimens be stored?

- e. Is the storage facility an on-site or off-site location?
- f. Will subjects be able to request that their specimen and/or information be withdrawn from the bank or repository? *(explain)*

### Section 13 – Children as Research Subjects

Research involving children must not be conducted by VA investigators while on official duty or at VA or VA-approved offsite facilities unless a waiver has been granted by the CRADO (See VHA Directive 2001-028 “Research Involving Children” for more information.

**92. Do you plan to enroll children as research subjects?**

**No** *(Proceed to Section 14)*

**Yes- Age range of subjects:**

**93. Category of Research** *(Check the box next to the category of research you believe your research falls under. The IRB will make a final category determination during review.):*

- Research involving minimal risk (the probability & magnitude of harm or discomfort anticipated are not greater than those ordinarily encountered in daily life or during routine physical or psychological tests.) (46.404)**
- Research involving greater than minimal risk but of potentially direct benefit to the subject. (46.405)**
- Research involving greater than minimal risk and no prospect of direct benefit to the subject but likely to yield generalizable knowledge about the subject’s disorder or condition. (46.406)**
- Research not otherwise approvable which presents an opportunity to understand, prevent or alleviate a serious problem affecting children/decisionally impaired adults. (46.407)**

**94. Do you anticipate enrolling minors who are wards of the state?**

**No**     **Yes**

**95. Permission of parents or guardian** *(check one only):*

- The permission of each child’s parents or guardian will be sought unless one parent is deceased, unknown, incompetent, or not reasonably available, or when only one parent has legal responsibility for the care and custody of the child (required for categories 46.406 and 46.407 above in item 104).**
- The permission of only one parent will be sought (acceptable for categories 46.404 or 46.405). If marked, provide justification:**

**96. Assent of Children** *(check one only):*

- The assent of each child who is capable of providing assent based on age, maturity, and psychological state will be sought.**
- The assent of each child will not be sought because the capability of all of the children in this study population is so limited that they cannot reasonably be**

consulted. Explain why the capacity is so limited, e.g., age, maturity and/or psychological state:

- The assent of each child will not be sought because the intervention or procedure involved in the research holds out a prospect of direct benefit that is important to the health or well-being of the children and is available only in the context of the research. Explain what the direct benefit may be and why it is only available in the context of the research:

#### Section 14 – Other

97. Please describe any other study procedures not referenced in the previous sections:

- Not applicable

Statistical Analysis Plan

Study Title: Cyclical muscle vibration in multiple sclerosis to improve walking

Last update: 01/29/2020

The within subject experimental design was used for this feasibility study because it requires fewer subjects with more statistical power while reducing the potential for systemic error or selection bias to test the effect of training with vibration on walking. While practice and carryover effects are major disadvantages of this study design, proper precautions including rest periods between tests and randomization of testing order for walking with or without vibration was instituted to minimize them at baseline and post-treatment¹. In this study design, any improvements at baseline with vibration compared to volitional gait can be attributed to short term effects of vibration. Improvements in volitional gait *post* training with vibration compared to volitional baseline gait can be attributed to long term effects of vibration. While this feasibility study design has limited generalizability due to the small number of subjects and inhomogeneity of the selected population, it can be quite useful for developing and refining future vibration intervention studies.

Means and standard deviations were calculated for all outcome measures for each subject. Differences in means were determined via a two-way analysis of variance ($p < 0.05$). A statistical power of 90% was used to determine the number of trials with VICON motion analysis system required for the testing and comparison of gait parameters. The results indicated a requirement of 30 strides of data or roughly 6 trials (approximately 5 strides per trial) for each condition (volitional or with vibration).

¹ Greenwald AG. With-in subject design: to use or not to use? *Psychological Bulletin*, 83(2):314-320, 1976.

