The primary goal of this pilot study is to explore the feasibility of cyclic vibration of the lower extremity muscles to improve walking in veterans with gait deficits from MS. Vibration is perhaps the most potent mechanical stimulus for activating muscle spindle primary afferents (Ia) [1]. This facilitates excitability of corticospinal projections to the target muscles while the  $\alpha$ -efferents to antagonists are inhibited. Since it has been shown that cyclical vibration promotes normal patterns of motor activity by modulating the excitability of motoneurons projecting to target muscles, *it is hypothesized that facilitatory effects of cyclical muscle vibration of hip, knee and ankle muscles improves 1) walking speed and foot-to-floor clearance through increased hip and knee pre-swing flexion and improved hip-knee coordination, 2) induces carryover effects that maintain improved walking after application and 3) produces no untoward sensations or adverse physiological responses.* In previous studies vibration to the dorsiflexor muscle tibialis anterior [2] alone and in combination with the hip abductor gluteus medius [3] resulted in improved walking speed in individuals with hemiplegia. Similarly, cyclical vibration increased muscle excitation with phase dependent changes in the timing of muscle activation during gait [4] and multi-channel complex vibration patterns exhibited gait-like leg movements that present a potential for rehabilitation [5].

Therefore, this pilot study is designed to explore the efficacy and safety of cyclical vibration at correcting the typical gait deficits that involve strength and coordination of multiple joints (hip, knee and ankle) in pre- and early swing and determine whether the new intervention warrants a full comprehensive study to quantify its facilitatory effects on gait improvement in veterans with MS.

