A one-way repeated measures ANOVA will be used to test for significant difference between means to test Hypotheses 1 and 2. The Tukey honestly significant difference multiple comparison test will be used between each pair of mean walking speeds, foot-to-floor clearance and maximum joint angles to determine 95% ( $p < 0.05$ ) confidence intervals for

statistically significant differences between conditions (CVN-VGB, CVN-VGP, VGP-VGB) and between groups to identify trends across all subjects.

† Greenwald AG. With-in subject design: to use or not to use? *Psychological Bulletin*, 83(2):314-320, 1976.

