### Gait evaluation after gait training

After twelve 2 hour sessions of gait practice with cyclical vibration emulating normal muscle activity of lower extremities, baseline speed and distance trials and VICON gait assessment with and without vibration will be repeated to test hypotheses. The primary outcome measures for testing hypotheses will be walking speed and foot-to-floor clearance as measured by vertical

Vibratory stimulation system with inserts showing size and mounting of vibrators over TFL- tensor fasciae latae, RF- rectus femoris, BF- biceps femoris, and TA- tibialis anterior (VSCU-Vibratory Stimulation Control Unit).

displacement of marker placed over the first metatarsal. Force sensing resistors (FSRs) will be used to detect any toe dragging as a result of insufficient foot clearance. Secondary measures will be peak hip, knee and ankle flexion during swing, hip-knee coordination changes, knee flexion during stance and in pre-swing and step length symmetry.

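### The SAP names a two-way ANOVA but no contrast for its short-term and long-term claims; on the vibration-by-time reading, the main effects equal those claims only if the interaction is zero

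*SAP*

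**What the plan says.** The first paragraph of the SAP sets out two inferences. The short-term one is that "any improvements at baseline with vibration compared to volitional gait can be attributed to short term effects of vibration". The long-term one is that "Improvements in volitional gait *post* training with vibration compared to volitional baseline gait can be attributed to long term effects of vibration". The same paragraph describes walking under both conditions at both visits: "randomization of testing order for walking with or without vibration was instituted to minimize them at baseline and post-treatment". The protocol (Section 3, item 13, gait evaluation after training) confirms that the fourth cell is measured: "VICON gait assessment with and without vibration will be repeated to test hypotheses".

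The second paragraph of the SAP gives the whole test specification: "Differences in means were determined via a two-way analysis of variance ($p < 0.05". It names no factors, interaction term, error term, simple-effect contrast or post-hoc procedure.

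The protocol (Section 3, item 10) specifies something else: "A one-way repeated measures ANOVA will be used to test for significant difference between means to test Hypotheses 1 and 2". It follows this with Tukey comparisons of three pairs of conditions. Two of the pairs are exactly the SAP's claims: vibration at baseline minus volitional baseline (CVN-VGB), and volitional post-training minus volitional baseline (VGP-VGB). The SAP neither repeats nor withdraws them. Hypothesis 2 (item 9) is that vibration "induces carryover effects that maintain improved walking after application". Neither document gives an expected value for walking with vibration after training.

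**The concern.** Each claim is a simple effect, that is, a difference between two particular cells of a two-by-two layout. A main effect in a two-way ANOVA averages such a difference over both levels of the other factor, so in general it is a different quantity. An analyst who has only the SAP would fit the ANOVA and could take the time effect as evidence on the long-term claim, although half of that effect comes from walking with the device switched on.

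Two things are at stake. The first is a false signal of carryover, which is Hypothesis 2. The treatment group trains for twelve sessions with vibration, so it is plausible that subjects would walk better with vibration while their unassisted gait stays the same. The second is the estimate itself. According to protocol item 11, the study exists to supply effect sizes for a larger trial, and an averaged effect would be the wrong quantity to carry forward.

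**Working it through.** **The plan's own figure.** The SAP gives 6 trials × about 5 strides = 30 strides per condition, and the multiplication is right. The 90% power behind it cannot be reproduced because no difference or SD is stated. It concerns strides, not subjects, and does not identify the contrast to be tested.

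**Cells.** Set volitional baseline to 0. Let S be vibration at baseline, L volitional post-training, and P vibration post-training. The claims are S (short term) and L (long term).

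- Vibration main effect = [(S − 0) + (P − L)]/2 = (S + P − L)/2
- Time main effect = [(L − 0) + (P − S)]/2 = (L + P − S)/2
- Interaction = P − L − S

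The vibration effect minus S is (P − L − S)/2, and the time effect minus L is also (P − L − S)/2. Each main effect therefore misses its claim by half the interaction.

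**Assumptions for size.** The documents give no effect size or SD, so these are mine: six treated subjects (protocol item 11), one mean per subject per cell, independent equal-variance within-subject errors, two-sided 5%, and effects in units of the SD of a paired difference between two cells. If each cell has error SD σ, a two-cell difference has SD σ√2 = 1 unit. A main-effect contrast has variance 4 × (1/4)σ² = σ², so its SD is 1/√2 = 0.707 units. With 5 df the noncentrality is:

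- two-cell contrast of size d: d√6
- main effect of size m: (m/0.707)√6 = m√12

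**Case 1: volitional gait unchanged (L = 0), P − S = g.** The time effect is g/2 and its noncentrality is g√3.

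| g (SD) | Noncentrality | Time effect significant | VGP-VGB contrast significant |
|---|---|---|---|
| 0 | 0 | 5% | 5% |
| 0.5 | 0.87 | 11% | 5% |
| 1.0 | 1.73 | 29% | 5% |
| 1.5 | 2.60 | 55% | 5% |
| 2.0 | 3.46 | 79% | 5% |

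**Case 2: both effects present (S = L = d), P = (1 + f)d.** Each main effect is d(1 + f)/2, with noncentrality d(1 + f)√3, against d√6 for the two-cell contrast. At f = 0 (full carryover and no added gain from vibration after training) the estimate is halved. The test statistic falls only by the factor √3/√6 = 0.71, because the main effect pools twice the data. The two tests break even at 1 + f = √2, so f = 0.41.

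| d (SD) | Two-cell contrast | Main effect, f = 0 | f = 0.5 | f = 1 |
|---|---|---|---|---|
| 1.0 | 51% | 29% | 55% | 79% |
| 1.5 | 83% | 55% | 87% | 98% |

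At f = 1 the interaction is zero and each main effect equals its claim.

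**Stride-level check.** Take 30 independent strides per cell in one subject and the difference that 30 against 30 strides would detect with 90% power, (1.960 + 1.282)√(2/30) = 0.837 SD of a stride. Both the independence and the difference are assumptions. Power is then 0.895 for the two-cell contrast, 0.62 for a main effect at f = 0 and 0.995 at f = 1. With volitional gait unchanged and P − S = d, the time effect is significant with probability 0.62. The pattern does not depend on the unit of analysis, although the percentages do.

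**The case against.** The strongest reply is that the SAP does not say main effects decide anything. Its factors are not named. Vibration by time is an inference, and subject by condition or group by time would also fit the words. A two-way ANOVA followed by comparisons of cells is routine and would test exactly these claims, and the protocol already plans the right pairs. On that view the SAP is brief rather than wrong. This stands in part: the documents show a missing specification and a mismatch between protocol and SAP, not a wrong test already committed to. It does not remove the need for a change. The SAP as written names no test of either claim. It also mentions no control group, which makes group by time a less natural reading of its text.

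A reader might go further and infer that the ANOVA halves both effects, and loses power, whenever both hypotheses are true. The documents do not support this. Halving needs S = L = P, and the hypotheses say nothing about P. Once the added gain with vibration after training exceeds about 0.41d, the main effect is the more powerful test.

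The false signal is conditional too. With volitional gait unchanged, the time effect departs from zero only if vibrated gait changes between visits, and nothing in the documents supports a change of 1.0 or 1.5 SD in particular. Finally, loss of power matters less in a feasibility study sized to gather preliminary data. Estimating the right quantity matters more.

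**Conclusion.** The concern holds in limited form. The SAP rests two conclusions on two-cell contrasts and names only a two-way ANOVA with unstated factors and no contrasts. If the factors are vibration and time, each main effect differs from its claim by half the interaction, and this algebra needs no assumption about size. The serious consequence is a time effect that could be reported as carryover when volitional gait has not changed: 29% of trials at a 1.0 SD gain confined to vibrated walking and 55% at 1.5 SD, against a nominal 5%, and still 5% if vibrated walking does not change. The effect on power can go either way: at d = 1.0 SD, 29% to 79% for f from 0 to 1, against 51% for the direct contrast. These percentages assume six subjects, a subject-level analysis, and independent equal-variance errors.

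**What to change.** Replace the ANOVA sentence in the SAP with a paragraph that does the following:

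1. Names the factors of any ANOVA that is kept, and the unit of analysis.
2. Makes two planned within-subject contrasts on subject means the tests of the two claims: with minus without vibration at baseline (CVN-VGB) for the short-term claim, and volitional post-training minus volitional baseline (VGP-VGB) for the long-term claim. These are the protocol's own comparisons.
3. Keeps a multiplicity adjustment, either the protocol's Tukey procedure or Holm, and says whether it covers both primary outcomes (walking speed and foot clearance).
4. Reports the vibration-by-time interaction with its confidence interval as a description of how the response to vibration changes, and bases neither claim on a main effect.

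The SAP should also say why the model differs from the protocol's one-way repeated measures ANOVA, or return to it. All four cells are already measured, so the cost is one paragraph and a rerun of the analysis, with no new data.
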